## **2.2 Dose Expansion Phase**

### **2.2.1 Primary Objective**

The primary objective in the dose expansion phase is to evaluate the anticancer activity of fruquintinib at the recommended Phase 2 dose (RP2D) from the dose escalation phase, in patients with advanced solid tumors.

### **2.2.2 Primary Endpoint**

The primary endpoint is PFS rate.

### **2.2.3 Secondary Objectives**

- To evaluate anticancer activity of fruquintinib, as assessed by ORR, DCR, DoR, PFS, and OS.
- To evaluate the pharmacokinetic (PK) characteristics of multiple-dose fruquintinib and investigate the metabolite profile of fruquintinib in plasma.
- To evaluate the safety of fruquintinib

### **2.2.4 Secondary Endpoints**

[figure not shown]
- The objective response rate (ORR), disease control rate (DCR), duration of response (DoR), PFS, overall survival (OS) and percentage change in tumor size from baseline according to RECIST Version 1.1.
- The primary PK parameters include maximum plasma concentration ( $C_{max}$ ), time to reach maximum concentration ( $T_{max}$ ), terminal half-life ( $t_{1/2}$ ), area under the concentration-time curve in a selected time interval ( $AUC_{0-t}$ ), area under the concentration-time curve in the time interval from 0 to infinity ( $AUC_{0-\infty}$ ), apparent clearance ( $CL/F$ ), apparent volume of distribution ( $V_z/F$ ) during the terminal phase according to  $CL/F/K_e$ , and the accumulation index based on AUC.
- Safety, as assessed by the incidence and severity of AEs, physical examinations, vital signs, laboratory test results, 12-lead electrocardiogram, and echocardiogram.

### 3 INVESTIGATIONAL PLAN

#### 3.1 Description of the Study

This is an open-label phase 1/1b study of fruquintinib comprised of a dose escalation phase that will enroll patients with advanced solid tumors of any type, and a dose expansion phase that will enroll patients with advanced solid tumors of any type (Cohort A), refractory mCRC (Cohorts B and C), or mBC (Cohorts D and E) (see study schema in [Figure 5](#).)

**Figure 5 Study Schema**

##### 3.1.1 Dose Escalation Phase

- Approximately 12 evaluable patients will be enrolled. The actual number of patients will depend on the occurrence of dose-limiting toxicities (DLTs) as well as the MTD level reached in this trial.
- The dose levels to be investigated are 3 mg and 5 mg QD, 3 weeks on/1 week off.
- Six DLT-evaluable patients will be enrolled in the phase and will be treated with fruquintinib 3 mg QD (3 weeks on/1 week off) orally. If no more than 1 DLT occurs during the DLT observational window (ie, from Days 1-28 in Cycle 1) among the 6 patients, the trial will continue to enroll another 6 patients in the next dose cohort in which fruquintinib 5 mg QD (3 weeks on/1 week off) will be tested.
- Safety monitoring and evaluation for the Dose Escalation phase will be carried out by the Safety Review Committee (SRC). Additional information about the SRC is provided in [Section 3.4](#).

- If no more than 1 patient at the dose level of 5 mg QD experiences a DLT, the dose escalation phase is completed and the expansion phase of the study will be conducted.
- Upon completion of the dose escalation/ phase, the SRC will review the aggregated safety and PK data and then select a fruquintinib dose as the RP2D for the expansion phase of the trial.
- Blood samples for PK assay will be collected in Cycle 1 at the following time points: pre-dose (within 10 minutes), 1, 2, 4, 8, and 24 hours post dose on Days 1, 14 and 21.
- Prior to confirmation of a DLT, if a patient has received any prophylactic medical intervention or missed 4 or more fruquintinib doses during the DLT observational window, the patient is not DLT evaluable and will be replaced.
- If a patient does not meet the definition of DLT evaluable patient criterion during the DLT observation period, the patient will be replaced.
- Patients who have completed the DLT observation period (Days 1-28, Cycle 1) and are deemed to be benefiting from the fruquintinib treatment at the investigator's discretion may continue the fruquintinib treatment until disease progression, death, intolerable toxicity, or at investigator's discretion that the patient can no longer benefit from the study drug.
- Please see [Appendix A](#) for the Schedule of Events and Section 5.2 for the dose modification instructions.
- Patients will be followed until death or study completion.

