	
 
• Blood samples for PK assay will be collected in Cycle 1 at the following time points: pre-dose (within 10 minutes), 1, 2, 4, 8, and 24 hours post dose on Days 1, 14 and 21.
 
• Prior to confirmation of a DLT, if a patient received medical intervention or missed 4 or more fruquintinib doses during the DLT observational window, the patient will not be qualified as DLT-evaluable and will therefore be replaced.
 
• If a patient does not meet the definition of DLT-evaluable patient during the DLT observation period, the patient will be replaced.
 
• Patients who have completed the DLT observation period (Days 1-28, Cycle 1) and are deemed to be benefiting from the fruquintinib treatment at the investigator's discretion may continue the fruquintinib treatment until disease progression, death, intolerable toxicity, or at investigator's discretion that the patient can no longer benefit from the study drug.
 
• Tumor evaluations during the dose escalation phase are scheduled at screening and every 8 weeks (<math>\pm</math> 1 week) thereafter, ie, C3D1, C5D1, C7D1, etc (odd-numbered cycles). Response assessments will be performed by the investigator using according to RECIST Version 1.1.
 
• Patients will be followed until death or study completion.
 
 
Dose Expansion Phase:
 
Once the RP2D is determined, patients may enroll into one of the following cohorts and will receive fruquintinib at the RP2D:
 
 
• Cohort A: Patients with advanced, refractory solid tumors of any type.
 
• Cohort B: Patients with refractory mCRC who have progressed on all standard chemotherapies and relevant biologics and have also progressed on, or had intolerable toxicity with, at least 1 FDA-approved third-line therapy (TAS-102 or regorafenib).
 
• Cohort C: Patients with refractory mCRC who have progressed on all standard chemotherapies and relevant biologics and have not received prior TAS-102 or regorafenib.
 
• Cohort D: Patients with hormone-receptor positive (ER+ and/or PR+)/Her2- metastatic breast cancer who have progressed on at least two line of prior systemic therapy.
 
• Cohort E: Patients with advanced triple negative breast cancer (TNBC) who have progressed on at least one cytotoxic therapy in the metastatic setting.
 
 
The safety of all enrolled patients in the expansion cohorts will be closely monitored from the first day of fruquintinib dosing until 30 days after the

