#### 1.3.1 Clinical Pharmacokinetics

The PK of fruquintinib was evaluated in patients with advanced malignant solid tumors treated with a single-dose or multiple-dose regimen (Study 2009-013-00CH1). Following administration, a single oral dose of 1, 2, 4, 5 and 6 mg, fruquintinib showed a very low clearance. The selection of the once daily (QD) dose regimen was justified by the terminal elimination  $t_{1/2}$  of >35 hours. The AUC and  $C_{max}$  generally increased dose-proportionally at the dose levels from 1 mg to 6 mg. Following multiple dosing, fruquintinib exposure reached steady state after QD administration for 14 days. Based on the AUC for the QD dosing interval (24 hours), accumulation of fruquintinib exposure from the first dose to steady state was approximately 3-fold.

The PK of a 4-week continuous dosing regimen of 5 mg QD was compared to a 3-week continuous dosing regimen of 6 mg QD followed by a 1-week break in fruquintinib therapy in patients with solid cancers (Study 2009-013-00CH1). The PK results showed that fruquintinib PK profiles were similar for the 2 dosing regimens on the same dosing days (see [Table 2](#)).

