### **c. Definition of a Dose-Limiting Toxicity**

- A DLT is defined as one of the toxicities defined for the primary endpoint of the dose escalation phase in Section 2.1.2. These AEs occur during the DLT assessment window (Days 1-28, Cycle 1) and are determined by the investigator to have a reasonable possibility of being related to fruquintinib.
- Any Grade 4 non-hematologic toxicity;
- Any Grade 3 non-hematologic toxicity related to study drug except for nausea/vomiting, diarrhea, constipation, hypertension and electrolyte imbalances downgraded within 3 days with appropriate supportive treatment;
- Grade 4 neutropenia lasting >3 days;
- Grade 3 febrile neutropenia (absolute neutrophil count [ANC]  $<1.0 \times 10^9/L$  with a single temperature of  $>38.3^\circ C$  or a sustained temperature of  $\geq 38^\circ C$  for more than 1 hour);
- Grade 4 thrombocytopenia or Grade 3 thrombocytopenia associated with bleeding;
- Dose interruption for >14 days due to toxicity;

In the absence of clinical abnormality, repeat laboratory testing will be conducted to confirm significant laboratory findings prior to designation as a DLT.

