**Table 8 Dose Modification for Hematologic and Non-Hematologic Toxicity**

NCI CTCAE v4.03 Toxicity Grading	Action
Grade 1 or 2 a	None
Grade 3 b	Interrupt the dose until the toxicity resolved to ≤Grade 1 or baseline level within 14 days, then reduce the dose to lower a dose level
Grade 4	Discontinue treatment permanently

a Should any arterial thrombosis occur, the treatment should be terminated.

b Including Grade 3 diarrhea and stomatitis, etc. that are ineffectively treated by drug therapies, but excluding Grade 3 menstrual cycle extension.

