**Table 14 Dose Adjustment for Abnormal Liver Function**

AE Grading a	Dose Adjustment	Treatment Suggestions
Grade 1	None.	Perform follow-up visit as scheduled.
Grade 2 or 3 (Liver function is abnormal but the biochemical criteria for Hy's Law b are not met)	
 
1. Drug interruption can be considered;
 
2. The dose should be reduced to the lower dose level if the AE recovers to Grade 1 or baseline within 14 days.
 
	Provide supportive care and increase the frequency of liver function monitoring to 1-2 times a week.
Grade 2 or 3 (Liver function is abnormal and the biochemical criteria for Hy's Law b are met)	The study drug should be terminated immediately.	Provide supportive care and increase the frequency of liver function monitoring to 2-3 times a week. Urgent medical intervention indicated.
Grade 4	The study drug should be terminated.	Urgent medical intervention indicated.

a Including increasing of ALT, AST, and total bilirubin, whether or not the biochemical criteria for Hy's Law have been met.

b Hy's Law is an increase in serum AST or ALT  $\geq 3 \times$  ULN together with total bilirubin  $\geq 2 \times$  ULN, and no other reason can be found to explain the biochemical changes, for example, new or worsening hepatobiliary metastases, elevated serum ALP indicating cholestasis, viral hepatitis, another suspect drug, or any other specific cause of severe hepatocellular injury. The elevation in transaminases must precede or be coincident with (ie, on the same day as) the elevation in total bilirubin, but there is no specified timeframe within which the elevations in transaminases and total bilirubin must occur. See Section 7.1.2 for special reporting requirements and Appendix H for additional information regarding Hy's Law.

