17.1. DLTs

A DLT is defined as one of the following toxicities occurring during the DLT assessment window (Cycle 1) and determined by the investigator to have a reasonable possibility of being related to fruquintinib. All DLT analysis will be performed for dose escalation phase only. In addition to summarizing the proportion of patients with DLTs, the DLT categories will also be summarized as follows:

- Any Grade 4 non-hematologic toxicity;
- Any Grade 3 non-hematologic toxicity related to study drug except for nausea/vomiting, diarrhea, constipation, hypertension and electrolyte imbalances downgraded within 3 days with appropriate supportive treatment;
- Grade 4 neutropenia lasting > 3 days;
- Grade 3 febrile neutropenia (absolute neutrophil count < 1.0 x 10⁹/L with a single temperature of > 38.3 °C or a sustained temperature of ≥38 °C for more than 1 hour);
- Grade 4 thrombocytopenia or Grade 3 thrombocytopenia associated with bleeding;
- DLT leading to dose interruption for > 14 days due to toxicity

The individual data of DLTs will also be listed by dose and/ or disease cohort and by patient.

Document: [REDACTED]

Author: [REDACTED] Version Number: 2.5
Version Date: 18Feb2022

Template No.: [REDACTED] Reference: CS_WI_BS005

Effective Date: 02Dec2019

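### DLT-evaluability rules drop and replace patients without a confirmed DLT even when doses were missed for toxicity, so the primary DLT incidence depends on tolerability in a direction the documents do not settle

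*Protocol*

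**What the plan says.** The primary endpoint of the escalation phase is the DLT incidence in each cohort (Protocol 2.1.2). A dose passes if at most 1 of 6 patients has a DLT (3.1.1 d).

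The replacement rule in Protocol 3.1.1 opens with "Prior to confirmation of a DLT, if a patient has received any prophylactic medical intervention" and extends to a patient who "missed 4 or more fruquintinib doses during the DLT observational window, the patient is not DLT evaluable and will be replaced". The reason for the missed doses plays no part. Section 3.1.1 b gives two routes to evaluability. One is to complete the 28-day cycle with full safety evaluations and 85% or more of the dose. The other is to have a DLT confirmed within that cycle.

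Section 3.1.1 c lists "Dose interruption for >14 days due to toxicity" as a DLT and places DLT events in Days 1-28. Section 5.2.1 allows toxicity holds of up to 14 days.

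The dose-modification tables act on some events outside the DLT list. Table 14 says "The study drug should be terminated immediately" for Grade 2 or 3 liver abnormality that meets the biochemical criteria for Hy's law. Table 8 says "Discontinue treatment permanently" at Grade 4.

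SAP 4.3 takes DLT evaluability from a CRF tick box. SAP 17.1 words the interruption item as "DLT leading to dose interruption for > 14 days due to toxicity", and SAP 2.4 does not list this among the changes from the protocol. The synopsis gives the replacement condition as "if a patient received medical intervention or missed 4 or more fruquintinib doses during the DLT observational window", without the word prophylactic.

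**The concern.** A DLT incidence is meant to describe how often patients cannot tolerate the dose. If some patients leave the DLT set because they could not tolerate it, the exclusion is informative, and with six patients per cohort one such exclusion matters. These patients are replaced, so the denominator returns to six and the loss does not show in the headline figure.

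The interruption criterion looks like the safety net, but it works poorly late in the cycle. Protocol 1.3.1 reports that "fruquintinib exposure reached steady state after QD administration for 14 days". Toxicity that appears only at full exposure would therefore tend to fall where the criterion is hardest to meet. The documents give no onset times, so this is a plausible pattern and not an observed one.

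**Working it through.** **1. The two exposure rules agree.** Table 7 (footnote) gives 21 doses per cycle. Three missed: 18/21 = 85.7%, which passes 85%. Four missed: 17/21 = 81.0%, which fails. Changing only one of the two rules would leave the exclusion in place.

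**2. Toxicities that stop or hold drug without being DLTs by grade.**
- ALT 4 x ULN with bilirubin 2.5 x ULN: each is Grade 2 in SAP Appendix 6 (ALT above 3 to 5 x ULN; bilirubin above 1.5 to 3 x ULN). Table 14 ends treatment. The non-hematologic DLT criteria start at Grade 3.
- Grade 4 neutropenia lasting 3 days or less: Table 8 ends treatment. The DLT needs more than 3 days.
- Grade 2 skin toxicity of the hands and feet, platelet decrease or hemorrhage (Tables 9, 12, 13): drug may be held. These patients reach the limit only if the hold covers at least four dosing days.

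**3. Timing.** Let s be the first missed day of a hold that lasts to the end of the cycle. Doses missed = 22 - s. Calendar days held by Day 28 = 29 - s.

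| s | Doses missed | Days held by Day 28 | 4 or more missed | More than 14 days by Day 28 |
|---|---|---|---|---|
| 14 | 8 | 15 | yes | yes |
| 15 | 7 | 14 | yes | no |
| 18 | 4 | 11 | yes | no |
| 19 | 3 | 10 | no | no |

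Holds from Days 15-18 therefore lead to replacement and cannot reach the criterion inside the window. For earlier holds the fourth dose is missed on Day s + 3 and the fifteenth day of the hold is Day s + 14, which is 11 days later. The replacement trigger comes first, and only the confirmed-DLT route in 3.1.1 b brings the patient back. Neither document says whether the planned week off counts toward the 14 days, whether a permanent stop counts as an interruption, or whether a hold is followed past Day 28.

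**4. Effect on the decision rule.** Assumed, not from the documents: p = proportion of treated patients with a listed DLT; q = proportion lost to toxicity without one. For event rate r, P(at most 1 of 6) = (1 - r)^6 + 6r(1 - r)^5. Replacement gives r = p/(1 - q); counting losses as events gives r = p + q; keeping them as non-events gives r = p. For p = 0.10 and q = 0.20, these are 0.10/0.80 = 0.125, 0.30 and 0.10.

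| p | q | Replaced | Counted as events | Kept as non-events |
|---|---|---|---|---|
| 0.10 | 0.05 | 0.875 | 0.776 | 0.886 |
| 0.10 | 0.10 | 0.863 | 0.655 | 0.886 |
| 0.10 | 0.20 | 0.833 | 0.420 | 0.886 |
| 0.17 | 0.10 | 0.683 | 0.487 | 0.729 |
| 0.25 | 0.10 | 0.469 | 0.319 | 0.534 |

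Replacement lies between the two alternatives in every row.

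**5. One hypothetical cohort.** With 1 DLT among 6 evaluable patients and one further patient replaced for toxicity, the primary figure is 1/6 = 16.7%. It is 2/7 = 28.6% if that patient counts as an event and 1/7 = 14.3% if kept as a non-event.

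**The case against.** A reader might infer that the primary DLT incidence is biased low. The documents do not support that as stated. Patients who meet no DLT criterion are non-DLTs by the protocol's definition, and dropping them raises the rate (0.10 to 0.125 above) and makes passing slightly harder (0.886 to 0.833). The 0.420 comes from relabelling them as events. The case for doing so is an analogy: a toxicity interruption of more than 14 days is a DLT, and a permanent toxicity stop seems at least as limiting. That justifies a sensitivity analysis, not a claim of bias.

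A reader might also infer that anyone who misses four doses is replaced. That is too broad. A confirmed DLT keeps the patient evaluable, and all Grade 4 and most related Grade 3 non-hematologic toxicities are DLTs themselves.

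Nor can it be said that the interruption criterion is impossible for later holds. Section 3.1.1 c requires the event to occur in Days 1-28 and could be read to allow follow-up beyond Day 28; only the confirmation clause in 3.1.1 b points the other way. A stricter cut-off from counting only dosing days (start by Day 7) rests on a count that the text does not state.

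Several safeguards exist. SAP 8.1 already tabulates reasons for exclusion from each analysis set. Other safety tables use all treated patients (SAP 4.2). The Safety Review Committee sees data from all enrolled patients (Protocol 3.4) and chose the dose on aggregated safety and PK data. DLT status was set at the time by the investigator and confirmed by the sponsor's medical monitor (Protocol 7.1.2). The recommended dose was declared before the current SAP version, so the SAP 17.1 wording cannot have affected escalation.

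All of this limits the consequence. It does not remove the missing toxicity exception, the undefined count of interruption days, or the unlisted SAP rewording.

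**Conclusion.** The point holds as a defect in how the primary DLT incidence is defined and reported. Patients without a confirmed DLT can be excluded and replaced because of drug-related toxicity, and the interruption criterion does not reliably recover them. If confirmation by Day 28 is required and calendar days are counted, the unreachable stretch for holds that still cause replacement is Days 15-18.

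The reported incidence understates dose-limiting intolerance if such stops are regarded as dose-limiting. If they are true non-DLTs, exclusion raises it slightly. The documents do not give the number of patients affected, so size and direction stay open. The probabilities above rest on assumed rates and show only that the choice can matter in cohorts of six. They do not show that the declared dose was wrongly chosen.

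Read as a definition, the SAP 17.1 item is circular, because an interruption alone could never create a DLT. It departs from the protocol without being declared.

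**What to change.** Because Protocol 5.1.6 shows escalation to be complete, the changes concern reporting and wording.

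1. In SAP 17.1, restore the protocol wording "Dose interruption for >14 days due to toxicity". State how interruption days were counted (planned week off, permanent stops) and whether a hold that began in the window was followed past Day 28.
2. Keep the primary DLT incidence. Add one sensitivity incidence per dose level, labelled post hoc. It returns to the denominator the patients excluded from the DLT set for drug-related toxicity (4 or more missed doses or a permanent stop), shown once as events and once as evaluable non-events.
3. In the existing SAP 8.1 exclusion table, give the toxicity behind each exclusion from the DLT set.
4. Reconcile the missed-dose rule in Protocol 3.1.1, the 85% rule in 3.1.1 b and the synopsis wording on medical intervention, and record which was applied.

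The cost is one small extra table for a phase planned at about 12 patients, from data already collected, plus SAP text. The drawback is a second DLT figure that may look less favourable.

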#### **a. Dose-Limiting Toxicity Assessment Window**

The DLT assessment window will be 28 days in the first cycle (Days 1-28). Any patient who is not considered evaluable for DLT as defined below will be replaced by an additional patient at that same dose level.

**NOTE:** Dose-limiting toxicity assessment does not apply to the expansion cohorts.

#### **b. Definition of DLT Evaluable Patients:**

A DLT evaluable patient has to meet the following criteria:

- Has not received any prior anti-cancer therapy prior to DLT; AND
- Has completed the first 28-day treatment cycle with complete safety evaluations and has received at least 85% of the assigned fruquintinib dose;

OR

- Has a confirmed DLT during the first 28-day treatment cycle.

### **c. Definition of a Dose-Limiting Toxicity**

- A DLT is defined as one of the toxicities defined for the primary endpoint of the dose escalation phase in Section 2.1.2. These AEs occur during the DLT assessment window (Days 1-28, Cycle 1) and are determined by the investigator to have a reasonable possibility of being related to fruquintinib.
- Any Grade 4 non-hematologic toxicity;
- Any Grade 3 non-hematologic toxicity related to study drug except for nausea/vomiting, diarrhea, constipation, hypertension and electrolyte imbalances downgraded within 3 days with appropriate supportive treatment;
- Grade 4 neutropenia lasting >3 days;
- Grade 3 febrile neutropenia (absolute neutrophil count [ANC]  $<1.0 \times 10^9/L$  with a single temperature of  $>38.3^\circ C$  or a sustained temperature of  $\geq 38^\circ C$  for more than 1 hour);
- Grade 4 thrombocytopenia or Grade 3 thrombocytopenia associated with bleeding;
- Dose interruption for >14 days due to toxicity;

In the absence of clinical abnormality, repeat laboratory testing will be conducted to confirm significant laboratory findings prior to designation as a DLT.

